## Analysis for efficacy variables

If otherwise not specified, the efficacy data will be summarized and analyzed with respect to core baseline only and will be presented by the core treatment group and visit. The mean, median, standard deviations, and range of each variable and its change from baseline measured on a continuous scale, will be presented by core treatment group and visit. Number and percentage of patients will be presented for categorical variables by core treatment group and visit. All hypothesis tests will be evaluated at a 0.05 level of significance, and the p-values will be rounded to the 4th decimal place. Change from baseline at Month X is defined as value at Month X - value at baseline. Percentage change from baseline is defined as 100 times the change from baseline divided by the baseline value. Missing values will not be imputed or replaced.

The efficacy variables and their analysis methods are described below.

- **Percent change in lumbar spine areal BMD Z-score at Months 18 and 24 relative to baseline, zoledronic acid group vs. placebo**

The percent change in LS-BMD Z-score at Months 18 and 24 relative to core baseline between zoledronic acid and placebo (the core treatment groups) will be evaluated using an ANCOVA model with core treatment, pooled center, underlying condition treated with glucocorticoids and core baseline LS-BMD Z-score as explanatory variables and pooled centers as random effect.

From the model, core treatment difference in least squares means between zoledronic acid group vs. placebo group will be estimated and presented together with two-sided 95% CI and p-value. In the same table, the LS means and standard errors for percent change from baseline in LS-BMD Z-score at Month 18 and Month 24 will be presented for each core treatment group. Descriptive statistics will also be shown for baseline, Month 18 and Month 24 visits.

- **Change in lumbar spine and total body BMC at Months 18 and 24 relative to baseline, zoledronic acid group vs. placebo**

The change in BMC at the lumbar spine and total body at Months 18 and 24 relative to core baseline between zoledronic acid and placebo will be evaluated using an ANCOVA model with core treatment, pooled center, underlying condition treated with glucocorticoids and core baseline BMC as explanatory variables and pooled centers as random effect.

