From the model, core treatment difference in least squares means between zoledronic acid group vs. placebo group will be estimated and presented together with two-sided 95% CI and p-value. In the same table, the LS means and standard errors for change from baseline in lumbar spine or total body BMC at Month 18 and Month 24 will be presented for each core treatment group. Descriptive statistics will also be shown for baseline, Month 18 and Month 24 visits.

- **Relative change in biochemical markers of bone turnover (Serum NTX, TRAP-5b, BSAP and P1NP) at Months 18 and 24 relative to baseline, zoledronic acid group vs. placebo**

The analysis of changes from core baseline to Month 18 and Month 24 in the biochemical markers, serum NTX, TRAP-5b, BSAP, and P1NP will be performed as follows: a transformation of the  $\log_e$  ratio of post-baseline value vs. baseline value at each visit will be used to normalize the distribution of the biochemical marker parameters. An ANCOVA model with core treatment group, pooled centers, underlying condition treated with glucocorticoids, and  $\log_e$  (core baseline value) as explanatory variables and pooled centers as random effect will be used on the transformed data at each post-baseline time point.

From the model, core treatment difference in least squares means between zoledronic acid group vs. placebo group in log scale will be estimated and presented together with two-sided 95% CI and p-value. Estimated core treatment difference and two-sided 95% CI will then be transformed back to the original scale and displayed on the table. In the same table, the LS means and standard errors in both log scale and original scale for change from baseline for the biomarkers at Month 18 and Month 24 will be presented for each core treatment group. Descriptive statistics will also be shown for baseline, Month 18 and Month 24 visits in both original scale and log scale. A plot will be generated for each biochemical marker over core and extension study period respectively.

- **Incidence of new vertebral fractures and new morphometric vertebral fractures during the 12 month extension period, zoledronic acid group vs. placebo**

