The number and percentage of patients with new vertebral fractures and new morphometric vertebral fractures during the 12 month extension period will be presented by core treatment group. Between-treatment differences will be evaluated using Fisher's exact test. New vertebral fractures are defined as fractures of Genant grade 1 or higher that occur at lumbar or thoracic spine from first extension dose infusion to the end of the extension study. New morphometric vertebral fractures during the 12 month extension period is defined as a morphometric vertebral fracture present at Month 24 X-ray which is not present at extension baseline.

- **Change in 2nd metacarpal cortical width at Month 24 relative to baseline, zoledronic acid group vs. placebo**

The change in 2nd metacarpal cortical width at Month 24 relative to core baseline will be evaluated using an ANCOVA model with core treatment, pooled center, underlying condition treated with glucocorticoids and core baseline bone age as explanatory variables and pooled centers as random effect.

From the model, core treatment difference in least squares means between zoledronic acid group vs. placebo group will be estimated and presented together with two-sided 95% CI and p-value. In the same table, the LS means and standard errors for change from baseline in 2nd metacarpal cortical width at Month 24 will be presented for each core treatment group. Descriptive statistics will also be shown for baseline and Month 24 visits.

[figure not shown]
Above analysis will be carried out with respect to both baselines (core baseline as well as extension baseline).

[figure not shown]
- **Reduction in pain from baseline, zoledronic acid group vs. placebo**

[figure not shown]
Pain is assessed using Faces Pain Scale-Revised (FPS-R) at first infusion in the extension study (Visit 9), Month 15, 18, 21 and 24, which ranges from 0 (No Pain) to 10 (Very Much Pain). Details of FPS-R can be found in Appendix section “Faces Pain Scale” in the protocol.

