## Analysis of covariance (ANCOVA) model

The following is an example of the SAS code used to perform these analyses.

```
ods output lsmeans=lsmeans
           diffs=lsmeandiffcl;
proc mixed data=xxx;
  class treat center gluco ;
  random center;
  model CHGVAR = treat center gluco BASVAR;
  lsmeans treat / pdiff=control ('1') alpha=.05 cl;
quit;
```

Adjusted change from baseline

Mean (SE): lsmeans.LSMean (lsmeans.STDERR)

Diff, 95% CI: lsmeandiffcl.DIFFERENCE (lsmeandiffcl.LowerCL, lsmeandiffcl.UpperCL)

p-value (pairwise): lsmeans.ProbtDiff

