## Logistic regression model

The following is an example of the SAS code used to perform these analyses.

```
ods output parameterestimates=EST oddsratios=ODDS;
proc logistic data=xxx descending;
format _all_;
  class treat center gluco/param=ref ref=first ;
  model RESP = treat center gluco BASVAR;
run;
```

Odds ratio: ODDS.oddsratioest where EFFECT contains 'treat'

95% CI for odds ratio: ODDS.LOWERCL and ODDS.UPPERCL where EFFECT contains 'treat'

P-value: EST.PROBCHISQ where VARIABLE='treat'

Note: In case of non-availability of enough patients, center effect will be dropped from all above statistical methodology.

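### The continuous efficacy ANCOVAs enter region as both fixed and random, so the per-arm LS-mean standard errors are undetermined; the metacarpal-width model also omits its own baseline.

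*SAP*

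**What the plan says.** The SAP, *Analysis for efficacy variables*, describes four continuous ANCOVAs. Each lists pooled center among the explanatory variables and then names it again as random. The LS-BMD Z-score model ends with "core baseline LS-BMD Z-score as explanatory variables and pooled centers as random effect", the BMC model has the same structure, and the bone-marker model reads "as explanatory variables and pooled centers as random effect will be used on the transformed data at each post-baseline time point". The metacarpal-width model has "underlying condition treated with glucocorticoids and core baseline bone age as explanatory variables and pooled centers as random effect". *Pooling of centers* defines four regions.

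The code under *Analysis of covariance (ANCOVA) model* follows the text: it has "random center" and also "model CHGVAR = treat center gluco BASVAR". Protocol 9.5.1.1, 9.5.1.2, 9.5.1.3 and 9.5.1.5 list pooled center once and mention no random effect.

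Per-arm results are a promised output. The LS-BMD text, for example, says "the LS means and standard errors for percent change from baseline in LS-BMD Z-score at Month 18 and Month 24 will be presented"; this is by core arm, and the other three endpoints have parallel wording. A note under *Logistic regression model* says: "In case of non-availability of enough patients, center effect will be dropped from all above statistical methodology". It gives no threshold.

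The LS-BMD, BMC and marker models adjust for the core baseline of their own outcome (log-transformed for markers). The metacarpal model, in the SAP and in Protocol 9.5.1.5, adjusts for bone age and not for baseline width. The SAP runs the metacarpal analysis against both the core and the extension baseline but names only core baseline bone age as covariate. BASVAR in the code is generic.

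**The concern.** A factor cannot usefully be fixed and random in the same model. The fixed region terms absorb all differences between regions, which leaves nothing from which to estimate a region variance. Software may still print one, and it feeds into the standard error of each arm's LS mean. A reader of the table could not tell whether that standard error reflects the data or a convergence setting.

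The metacarpal issue is separate. A change score that is not adjusted for its own baseline generally loses precision, and it leaves any chance imbalance in baseline width uncorrected among the core completers who enter the extension. Because the covariate for the extension-baseline run is not stated, a programmer would have to choose it.

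**Working it through.** The documents give no standard deviation, effect size or power for these endpoints, so there is no planned figure to reproduce. The checks are algebra plus simulated data; the simulation inputs are assumptions.

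**1. Region entered twice**

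Write y = Xb + Zu + e, with region indicators in both X and Z. REML uses only contrasts K'y with K'X = 0. Since the columns of Z lie in the column space of X, K'Z = 0 as well, so the REML likelihood does not contain the region variance s_c². The fixed-effect estimates equal ordinary least squares. With equal weight on four regions:

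Var(LS mean) = Var(LS mean, region fixed only) + s_c²/4.

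The extra term is common to both arms and cancels in the treatment difference.

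Simulated data used four unequal regions, three underlying conditions and one baseline covariate. The region/residual variance ratio was set in turn to five values:

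| Ratio | One arm's LS-mean SE, N=80 | One arm's LS-mean SE, N=40 |
|---|---|---|
| 0 | 0.195 | 0.263 |
| 0.05 | 0.231 | 0.287 |
| 0.2 | 0.314 | 0.349 |
| 1 | 0.583 | 0.578 |
| 5 | 1.243 | 1.180 |

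The REML log-likelihood was −54.3978 in every N=80 row and −25.475 in every N=40 row. The treatment SE was 0.258 and 0.351 throughout. Check against the formula at N=80, ratio 5, where s_c² = 6.03: √(0.195² + 6.03/4) = 1.243.

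An actual REML mixed-model fit (separate simulated data, N=80) from three starting values gave region variances of 0.0001, 0.318 and 31.8. The log-likelihood was the same each time (−122.970), as was the treatment SE (0.256). The per-arm SEs were 0.185, 0.338 and 2.828.

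**2. Metacarpal width without its own baseline**

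Assume a baseline/Month-24 correlation ρ and a ratio k of the Month-24 SD to the baseline SD. With baseline variance 1 and ignoring bone age:

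- Var(change) = 1 + k² − 2ρk
- Residual variance after adjusting for baseline = k²(1 − ρ²)
- Reduction in SE = 1 − √(residual variance / Var(change))

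| ρ | k | Var(change) | Residual variance | SE reduction |
|---|---|---|---|---|
| 0.5 | 1 | 1.000 | 0.750 | 13.4% |
| 0.7 | 1 | 0.600 | 0.510 | 7.8% |
| 0.9 | 1 | 0.200 | 0.190 | 2.5% |
| 0.5 | 1.1 | 1.110 | 0.908 | 9.6% |
| 0.7 | 1.1 | 0.670 | 0.617 | 4.0% |
| 0.9 | 1.1 | 0.230 | 0.230 | 0.0% |
| 0.8 | 1.2 | 0.520 | 0.518 | 0.2% |

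Without adjustment, a baseline imbalance carries into the treatment difference with weight |1 − ρk|. That is 0.50 at ρ = 0.5, k = 1, and 0.01 at ρ = 0.9, k = 1.1.

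With bone age also in the model, 108 assumed correlation sets were examined. Adding width never raised the residual variance. Replacing bone age by width raised it by up to 36%.

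**The case against.** **The effect is limited.** The treatment difference, interval and p-value are untouched by the double entry, and all of this is secondary to a safety objective. That is correct and limits the weight of the point.

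**No wrong SE has been shown.** The fits were not run in SAS PROC MIXED, the procedure in the example code. A program that sets the region variance to zero would print the fixed-region SE. The table of ratios therefore shows indeterminacy, not an expected error. This stands, but the SAP does not specify such a convention.

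**The text may only be saying which listed term is random.** That reading is possible for the prose. It does not rescue the code, which has center in both statements.

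**Region could legitimately be random instead.** In a simulation with N=100, random-only entry gave a per-arm SE of 0.285 against 0.173 for fixed-only, with treatment SEs of 0.2059 and 0.2065. Either single entry is determinate, and the protocol does not use the word fixed. Fixed is nevertheless the ordinary reading of the protocol's ANCOVA and is sound with only four regions.

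**Bone age was prespecified consistently in both documents, and the gain from width depends on assumptions.** Both statements are true. The SE reductions above ignore bone age, so they are not figures for the planned model. With bone age retained, the gain can be zero or larger than those shown. That adding a covariate does not raise residual variance holds by construction. Omitting width does not bias the core comparison in expectation.

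**Some efficacy subsections are blacked out.** The statement that this model alone lacks its own baseline therefore applies to the visible ANCOVAs.

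**Conclusion.** Both parts hold. As written, the per-arm LS-mean standard errors for LS-BMD Z-score, BMC, bone markers and metacarpal width are not determined by the data. The flat likelihood and the s_c²/4 term are algebraic and do not rest on the simulation settings; the particular SE values do. Between-group inference is unaffected. The note allowing center to be dropped would remove the problem only when invoked, and it has no trigger.

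For metacarpal width, omitting the outcome's own baseline costs an unknown amount of precision: 0% to 13.4% in SE over the assumed values of ρ and k, ignoring bone age. It also leaves chance imbalance in the core-baseline run unadjusted. The correction should be made because it costs almost nothing, not because it threatens the trial's main conclusion.

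**What to change.** 1. In the four ANCOVA descriptions, delete the clause that makes pooled centers random, and remove the RANDOM statement from the example code. Region then stays fixed, in line with Protocol 9.5.1.1 to 9.5.1.3 and 9.5.1.5.
2. State the number of patients per region below which center is dropped.
3. In the metacarpal model, add baseline 2nd metacarpal cortical width alongside bone age, not in its place. Take it from the baseline that matches the change analysed (core or extension).
4. Define BASVAR for each endpoint and each run.
5. Label the extension-baseline metacarpal comparison as descriptive, because a difference in width between arms at that point may already be an effect of core treatment.

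The cost is SAP wording, one deleted code line and one model degree of freedom for metacarpal width, which raises the 95% t critical value by about 0.1% at N=40. No new data are needed: baseline width is already tabulated (SAP, *Demographic and other baseline characteristics*), and the hand X-ray is repeated at the last Core visit (Protocol 6.4.6).

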### **Other analyses**

The following core data for the patients in the extension FAS will be summarized and analyzed similarly at core visits to give an overall profile during the 24 months core and extension combined period:

- Change in LS-BMD Z-score relative to baseline
- Change in lumbar spine and total body BMC relative to baseline
- Relative change in biochemical markers of bone turnover (Serum NTX, TRAP-5b, BSAP and PINP)
- Change in 2nd metacarpal cortical width relative to baseline

### **Pharmacokinetic (PK) evaluations**

Not applicable.

## Safety evaluation

All safety analyses will be performed on the SAF. The assessment of safety will include adverse events, laboratory tests (hematology, blood chemistry and urine values), vital signs, and tanner staging score. Patient listings will be provided for all safety data.

## Analysis for the primary objective

The primary objective is to demonstrate that zoledronic acid given long-term, over an additional 12 months from the Core study (CZOL446H2337), is safe for the treatment of osteoporotic children treated with glucocorticoids.

## Adverse events

An adverse event (AE) is any untoward medical occurrence in a subject or clinical investigation subject after starting the study drug even if the event is not considered to be related to study drug. Treatment-emergent adverse events will be defined as adverse events that were absent prior to the first infusion in the extension study and occurred after the first infusion during extension study or that were present prior to the first infusion in the extension study and occurred at increased severity after the first infusion during extension study. Summarization will be based on treatment-emergent adverse events.

Adverse events will be coded using the Medical dictionary for regulatory activities (MedDRA). The number and percentage of patients who report adverse events will be summarized by treatment according to the primary system organ class and preferred term. If a patient reports more than one adverse event within the same primary system organ class (preferred term), the patient will be counted only once with the greatest severity at the system organ class (preferred term) level. Serious adverse events and selected adverse events will be presented by core treatment group code. Listing of these events will be provided.

Adverse event tables will be sorted alphabetically by system organ class and then according to decreasing frequency of preferred term in the zoledronic acid group. If only system organ classes or preferred terms are presented, these will be sorted according to the decreasing frequency in the zoledronic acid group.

The following sets of adverse events will be summarized:

- All adverse events (by primary system organ class and preferred term)
- Adverse events suspected to be related to study drug (by primary system organ class and preferred term)
- Adverse events that occurred after first infusion in the extension study and before second infusion in the extension study (by primary system organ class and preferred term)
- All adverse events (by primary system organ class, preferred term and maximum severity)

- All adverse events (by underlying disease group, primary system organ class and preferred term)
- Adverse events that result in death (by primary system organ class and preferred term)
- Serious adverse events (by primary system organ class and preferred term)
- Adverse events causing permanent discontinuation of study drug (by primary system organ class and preferred term)
- Adverse events causing concomitant medication taken (by primary system organ class and preferred term)
- Adverse events associated with a change in renal function (by preferred term). Time from first infusion in the extension study to first adverse event associated with a change in renal function will be presented separately.

- █ [REDACTED]
- Hypocalcemia adverse events (by preferred term). Time from first infusion in the extension study to first hypocalcemia occurrence based on AE and central lab calcium will be presented separately.

Incidence of risk as defined in the case retrieval strategy, during the study period, will be summarized by core treatment group, and MedDRA levels. Relative risk of zoledronic acid group vs. placebo (core treatment A vs. core treatment B) will be presented along with corresponding 95% confidence intervals using the Mantel-Haenszel test.

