Visit 8 A will serve as the first (screening) visit for Group 2. Patients will return at Visit 9 and all patients will receive zoledronic acid. The allowed screening window between Visit 8 A and Visit 9 is 30 days. Central labs from Visit 8 A will be utilized for Visit 9, provided the lab samples have been collected within 30 days prior to the Visit 9 infusion. Otherwise, the labs must be redrawn and the results reviewed for eligibility, prior to infusion at Visit 9. The DXA scans (hip, spine and distal femur) and X-rays collected at Visit 8 A will be read centrally and if the child/adolescent is eligible, used for Baseline provided the DXAs have been obtained within 3 months of Visit 9; otherwise, the DXA scans must be repeated at Visit 9.

All Patients (Group 1 and Group 2) will receive two infusions of i.v. zoledronic acid (0.05 mg/kg) with an interval of 6 months at Visit 9 and at Visit 12.

Safety and efficacy will be assessed at 6 (Visit 12) and 12 months (Visit 15), with additional visits 10 days after each infusion to evaluate on renal and calcium (Visit 10 and 13) as well as

telephone visits to assess pain, adverse events [REDACTED] and concomitant medication at 3 (Telephone Visit 11) and 9 (Telephone Visit 14) months.

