3.2 Rationale of study design

The study is an open-label study where all patients will be receiving active study drug (zoledronic acid 0.05mg/kg).

Group 1: The Core study, CZOL446H2337, is part of a Pediatric Investigational Plan (EMA-000057-PIP01-07), [REDACTED]. This one-year study will extend the period of observation in patients who have completed the Core protocol and will collect long-term safety and efficacy data (Group1). The primary objective of the study will focus on general safety. The Extension study is an open-label study where all patients will receive active study drug (zoledronic acid 0.05 mg/kg). Given the rapid bone loss associated with the use of GCs and the fracture inclusion criteria for enrollment in the Core study, an open-label study design addresses ethical considerations for those patients who were randomized to receive placebo in the Core study who may deteriorate and require an active intervention, while at the same time allowing for the primary objective to be assessed.

Group 2: The study will capture additional safety and efficacy data on zoledronic acid from patients who presented with clinically significant back pain (significant symptoms) from vertebral fracture who were not enrolled into the Core study (Group 2) because the pre-existing clinical care at the Investigator's site is to treat this type of patient with a bisphosphonate.

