5.1.2 Additional treatment

Adequate intake of vitamin D and calcium is mandatory for the four weeks prior to randomization and throughout the duration of the study, either through adequate dietary intake or via supplementation, or a combination of both diet and supplementation. Described below are the recommended guidelines for vitamin D and calcium intake. It is the responsibility of the investigator to ensure that each patient receives the adequate recommended daily allowance (RDA) of vitamin D and calcium (through diet and/or supplementation)([Ross et al 2011](#)).

Table 5-1 Recommended minimum daily dietary allowances

Age	Vitamin D	Calcium
≥ 5 years to ≤ 8 years	600 IU	1000 mg
≥ 9 years to ≤ 20 years	600 IU	1300 mg

All patients should take at least 600 IU vitamin D daily from Visit 8/8A until the final extension study visit through diet and/or supplementation.

Elemental calcium, at least 1000 mg for 5-8 years of age or at least 1300 mg for 9-20 years of age, daily will be taken beginning at Visit 8/8A and during the total duration of the trial, through diet and/or supplementation. Calcium carbonate is the preferred form of calcium

supplementation. If calcium carbonate is not well tolerated, another form of oral calcium would be acceptable.

Any vitamin D and calcium supplements will be recorded on the Concomitant medications/Significant non-drug therapies eCRF.

In addition, transient hypocalcemia has been reported following the first infusion and it can cause symptoms in rare cases. To prevent the development of symptomatic hypocalcemia, the parent or legal guardian of each child will receive an information sheet and all patients will receive calcium supplementation at the doses recommended in [Table 5-1](#) starting at least from the day of infusion and for a minimum of 5 days after the infusion (for sites where this calcium supplementation usually starts prior to the infusion, the total treatment period is approximately 10 days in total) ([Hogler et al 2004](#)).

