5.2 Treatment arms

All patients will be given open-label zoledronic acid.

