5.5.7.1 Treatment of study drug related adverse events

As with other bisphosphonates, zoledronic acid has been associated with post-dose symptoms that may include fever, nausea, myalgia, arthralgia and bone pain, with onset occurring within the first 72 hours after the infusion. Typically these symptoms occur with the first infusion of bisphosphonate. The symptoms are usually mild to moderate and rarely severe. These symptoms may be adequately managed, at the discretion of the investigator, with non-steroidal anti-inflammatory agents (e.g. acetaminophen/paracetamol or ibuprofen) and/or anti-

emetics by local treatment standards and according to approved local labeling. Based on data from controlled trials, treatment with non-steroidal anti-inflammatory agents will reduce the incidence of these symptoms by approximately 50%. In managing these symptoms it is important to encourage adequate hydration and food intake. An anti-emetic may be provided to reduce the risk of symptomatic hypocalcemia if the child develops nausea or starts to vomit. Further calcium supplements will be provided for up to 10 days at the time of infusion and parent or legal guardian instructions provided on the signs to watch for as well as an emergency number, if needed.

All dosages prescribed and dispensed to the patient and all dose changes during the study must be recorded on the concomitant medications/significant non-drug therapies eCRF after start of study treatment.

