### **Hypocalcemia adverse events and laboratory events**

Hypocalcemia adverse events will be searched based on preferred term and summarized. Patients with reported laboratory measurements associated with a signal of hypocalcemia will be summarized by visit. Lab hypocalcemia (low serum calcium levels) is present if the value of serum calcium from central lab is less than the lower limit of normal range provided by the central lab.

The number and percentage of patients who met these criteria will be summarized by core treatment group and overall.

The hazard ratio, 95% CI and p-value based on a Cox proportional hazards model with core treatment and underlying condition treated with glucocorticoids (stratification factor) as explanatory variables will be presented. Meanwhile, to aid in the assessment that the treatment differences are not inconsistent across the strata, the treatment-by-stratification interaction term will be added to the model described above. P-value for the interaction term will be reported. If a patient experiences a hypocalcemia and low calcium value based on the central lab, the event time is defined as the earlier of these events. Otherwise, a patient is considered censored at the last contact date. Kaplan-Meier estimates will be plotted over time if at least 10% of overall population has experienced the event.

Patient listings will be provided for all adverse events associated with hypocalcemia.

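### The planned relative risk 'vs. placebo' and the hazard ratios by core treatment compare continued with newly started zoledronic acid, and for hypocalcemia first-infusion events are expected to push the ratio below 1

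*SAP*

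**What the plan says.** Treatment is the same for everyone in the extension. Protocol 5.2 states: "All patients will be given open-label zoledronic acid". Protocol 3.1 adds that all patients "will receive two infusions of i.v. zoledronic acid (0.05 mg/kg) with an interval of 6 months at Visit 9 and at Visit 12". Protocol 3.2 gives as one reason for the open-label design the needs of "those patients who were randomized to receive placebo in the Core study". Those patients therefore start active drug here.

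The SAP's Safety Analysis Set groups patients by what they received in the Core study. Its Adverse events section bases the summaries on treatment-emergent events: "adverse events that were absent prior to the first infusion in the extension study" and occurred after it, or were present before and became more severe after it.

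Two kinds of between-group estimate follow.

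- In the Adverse events section, for the risks in the case retrieval strategy: "Relative risk of zoledronic acid group vs. placebo (core treatment A vs. core treatment B", with 95% confidence intervals by Mantel-Haenszel.
- In the sections on renal adverse events and on hypocalcemia: "The hazard ratio, 95% CI and p-value based on a Cox proportional hazards model with core treatment" and underlying condition as explanatory variables. Time runs from the first extension infusion.

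On timing of risk, Protocol 5.5.7.1 says of the post-dose symptoms: "Typically these symptoms occur with the first infusion of bisphosphonate". Protocol 5.1.2 says "transient hypocalcemia has been reported following the first infusion". Protocol 3.6 also describes acute phase reactions as more common after the first infusion.

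**The concern.** A ratio described as zoledronic acid against placebo will be read as the effect of the drug. No group in the extension is untreated, so the ratio cannot be that. It contrasts patients already exposed in the Core study with patients having their first exposure.

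For events that concentrate at the first infusion, the former placebo group carries the excess inside the counting window. The other group had its own first infusion in the Core period, outside the window. A ratio below 1 is then what the design produces, and a reader could take it as reassurance about the drug. Harm shared equally by both groups does not appear in the ratio at all. Nothing in the SAP tells the reader how to interpret a value below 1.

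**Working it through.** The plan states no event rate, effect size or power for these comparisons, so there is no figure of its own to reproduce. The check has three parts.

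**1. Which infusion is being counted.** The Core regimen was two infusions six months apart (Protocol 3.3).

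| Core group | Core period | Visit 9 | Visit 12 |
|---|---|---|---|
| Zoledronic acid, both Core doses | infusions 1 and 2 | 3 | 4 |
| Placebo | none | 1 | 2 |

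A patient with only one active Core dose would be at infusions 2 and 3. In either case, only the placebo row has infusion 1 inside the window.

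**2. Direction.** Let b be the 12-month background risk without drug, r1 the added risk at a patient's first zoledronic acid infusion, and r2 the added risk at any later one (taken as constant).

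- Continuing group: p_c = 1 − (1 − b)(1 − r2)²
- Newly started group: p_n = 1 − (1 − b)(1 − r1)(1 − r2)
- RR = p_c / p_n, and HR ≈ ln(1 − p_c) / ln(1 − p_n)

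p_c is smaller than p_n exactly when (1 − r2) > (1 − r1), that is, when r1 > r2. Background risk does not affect the direction. The protocol's statements suggest r1 > r2 for acute reactions and hypocalcemia. It says nothing of the kind for renal events; if their risk rose with repeated exposure, that ratio would exceed 1.

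**3. Size, with assumed rates only.**

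Simplest case, 10% at repeat infusions against 30% in former placebo patients, log-scale 95% CI:

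- 50 per arm: RR = (5/50)/(15/50) = 0.33; SE = √(1/5 − 1/50 + 1/15 − 1/50) = 0.476; CI 0.13 to 0.85.
- 30 per arm: RR = (3/30)/(9/30) = 0.33; SE = √(1/3 − 1/30 + 1/9 − 1/30) = 0.615; CI 0.10 to 1.11.

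Fifty per arm is an upper bound under equal allocation, because Protocol 9.6 expects about 100 patients across Groups 1 and 2 together.

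With background risk and both infusions included:

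| b | r1 | r2 | p_c | p_n | RR | HR | 95% CI for RR, 40 per arm |
|---|---|---|---|---|---|---|---|
| 5% | 15% | 5% | 14.3% | 23.3% | 0.61 | 0.58 | 0.24 to 1.58 |
| 5% | 30% | 10% | 23.1% | 40.2% | 0.57 | 0.51 | 0.29 to 1.13 |
| 5% | 50% | 10% | 23.1% | 57.3% | 0.40 | 0.31 | 0.22 to 0.75 |
| 10% | 50% | 20% | 42.4% | 64.0% | 0.66 | 0.54 | 0.43 to 1.02 |
| 5% | 10% | 10% | 23.1% | 23.1% | 1.00 | 1.00 | 0.45 to 2.23 |

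Over the eight scenarios run with r1 > r2 (b 5% or 10%, r1 15% to 50%, r2 5% to 20%), the planned RR is 0.40 to 0.69. In the same scenarios the risk relative to an untreated year is p_n/b = 2.7 to 12.4 for newly started patients and p_c/b = 1.9 to 7.8 for continuing patients. In the last row the planned RR is 1.00 although the drug raises risk 0.231/0.05 = 4.6-fold; with b = 10% the corresponding figure is 0.271/0.10 = 2.7-fold.

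**The case against.** Much can be said for the plan, and most of it stands.

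- **The contrast is not hidden.** The relative-risk sentence glosses its groups as core treatments, and the SAP tabulates by core treatment throughout. A reader might infer that all the ratios are labelled as placebo comparisons with p-values. Only the relative-risk sentence says placebo, and it mentions no p-value; the Cox sections say core treatment.
- **The ratios decide nothing.** The SAP's section on statistical model and method calls the analysis descriptive, and Protocol 9.4.1 limits any tests to highlighting comparisons. No success criterion rests on them, so they are not the basis of the primary safety conclusion.
- **Core-period events are not lost.** They leave the treatment-emergent tables if they persist unchanged. The SAP's medical history section still tabulates them by core treatment, and Protocol 9.2 adds those still present at the first extension infusion.
- **Some helpful tables exist.** Adverse events between the two extension infusions are tabulated. Hypocalcemia is summarized overall as well as by group, and laboratory hypocalcemia by visit. Laboratory changes use both baselines.
- **Repeat against first exposure is not meaningless.** It bears on longer exposure, though first-infusion effects are mixed into it.
- **The acute-reaction example may not arise.** The case-retrieval risks are not listed and one bullet is blacked out, so a relative risk for acute reactions cannot be confirmed.

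What remains is the label, the missing statement of meaning, and the lack of alignment by infusion number. Calling the analysis descriptive does not cure these, and the Cox p-values sit awkwardly with that word.

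**Conclusion.** The point holds in a limited form. The relative risk is mislabelled, and all these ratios estimate continued against newly started zoledronic acid. For hypocalcemia, which has its own hazard ratio and p-value, a value below 1 is expected from the design, provided first-infusion risk exceeds later risk as the protocol's text suggests. The same would apply to an acute-reaction ratio if one is produced.

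A reader might infer that every ratio, including the renal one, is biased towards making the drug look safe. The documents do not link renal events to the first infusion, so that direction is open. A reader might also infer that a significant protective effect is likely. The documents give no rates, Group 1 size or Core allocation; at the same assumed rates the interval excludes 1 with 50 per arm and includes it with 30. The part that does not depend on these assumptions is that none of the ratios can estimate drug against placebo.

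**What to change.** In the SAP:

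1. Label the groups 'zoledronic acid to zoledronic acid' and 'placebo to zoledronic acid' in the safety tables.
2. In the Adverse events section, replace the placebo wording of the relative risk with 'continued vs newly started zoledronic acid'. There, and in the renal and hypocalcemia sections, state that the ratio is not a drug-versus-placebo effect.
3. Drop the hazard-ratio p-values, so that these sections agree with the descriptive statement.
4. Add pooled incidence in the whole Safety Analysis Set for the risks that lack it.
5. Add incidence by infusion number, counted from each patient's first zoledronic acid infusion, using Core adverse event and laboratory data for the core zoledronic acid group.

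The cost is SAP wording and a few extra tables from data the sponsor already holds. No new data collection is needed.
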